1 **Casting without Reduction versus Closed Reduction with or without Fixation in the Treatment**  
2 **of Distal Radius Fractures in Children: A Study Protocol for a Randomized Non-Inferiority Trial**

3  
4 *Background*

5  
6 Fractures are prevalent in the pediatric population. It is estimated that one in three children will  
7 sustain at least one fracture before adulthood, of which distal metaphyseal radius fractures are  
8 the most frequent[1, 2]. Current treatments include *in situ* cast immobilization, or reduction  
9 with or without fixation with K-wires, decided upon angulation and displacement. Traditionally,  
10 specific deformity limits are tolerated, given the child's age and gender, however, these limits  
11 lack supportive evidence. Further, treatment agreement, even between experienced pediatric  
12 orthopedic surgeons, is minimal[3].

13  
14 Distal radius fractures have a remarkable remodeling potential. The remodeling rate is higher  
15 when the angulation is more severe, and it progressively decreases as the alignment  
16 approaches to normal[4]. Observational designs have shown that fractures up to 29 degrees of  
17 angulation and 19 mm of shortening immobilized *in situ* regain complete alignment about a  
18 year after injury[5]. Even shorter times to proper alignment are reported in younger children[5].  
19 Additionally, Crawford et al. describe a series of children treated with cast immobilization  
20 without restoring the length of the radius, achieving neutral ulnar variance at follow-up[6].  
21 Furthermore, when alignment is lost, typical radius morphology is present within three years

22 even when the fracture is immobilized without any attempt to regain alignment[7]. Hence,  
23 casting without reduction is considered a suitable treatment.

24

25 Some specialized centers reserve distal radius corrective osteotomy solely for fracture  
26 malunion in children approaching the end of growth or with associated physal arrest. It is also  
27 the treatment of choice for children with congenital dysplastic conditions of the bone[8].

28

### 29 *Functional evaluation*

30

31 Upper extremity functionality refers to reaching, grasping, and manipulating objects with the  
32 intention to perform daily life activities[9]. Most of the instruments that assess upper extremity  
33 functionality in the pediatric population are specific to patients with longitudinal deficiencies,  
34 amputations, or neurodevelopmental disorders. Specific instruments for adults have also been  
35 published, however, several items refer to tasks that a 5-year-old child might not be able to  
36 properly execute.

37

38 The physical functioning domain of the PROMIS scales is available for assessing functionality of  
39 children without disabilities since 2011[10]. It is a precise and easy-to-administer outcome  
40 measurement instrument in children with orthopedic conditions. Children aged 8 years  
41 onwards are able to, effortlessly, answer the questionnaire by themselves. A parent-proxy  
42 version is available for younger children. The upper extremity functionality is a subdomain of

43 the physical functioning domain. It comprises 29 Liker-type questions with five categories that  
44 enquire about the difficulty of carrying out activities during the past week.

45

46 The trial's primary goal is to establish whether upper extremity's functionality of children who  
47 sustained a distal metaphyseal fracture of the radius and were treated with *in situ* cast  
48 immobilization, is not worse than the functionality of children treated with closed reduction  
49 and cast immobilization, with or without fixation, measured at 6 months with the PROMIS  
50 scale. Secondly, range of motion (ROM), alignment, complications and further treatments  
51 will also be compared. Results may contribute to not only strengthening the evidence of secure  
52 shortening and angulation boundaries, aiding the clinician with evidence-based decision, but  
53 risks and costs may also be questioned, when encountering these kinds of fractures.

54

## 55 **Methods**

56

### 57 *Study design and procedures*

58

59 This is a randomized non-inferiority trial that will take place at Instituto Roosevelt in Bogota–  
60 Colombia, a single institution that focuses on providing treatment for children with orthopedic  
61 and neuromuscular conditions. Two accepted treatments for metaphyseal distal radius  
62 fractures will be compared: cast immobilization without reduction as the experimental  
63 intervention, and closed reduction and immobilization with or without percutaneous fixation as  
64 the control intervention. Acutely, conventional oral analgesics will be routinely provided,

65 afterwards, the principal researcher will invite children and parents to enter into the trial upon  
66 confirming admission criteria. Informed consent, along with informed assent, will be signed.

67

68 *Inclusion criteria*

69

70 Children between 5 to 10 years of age with a proven acute (i.e., within 14 days after injury)  
71 metaphyseal fracture of the distal radius (23-M 2-3 or 23r-M 2-3 according to the AO pediatric  
72 classification) will be regarded as eligible for the trial. Fracture shortening and angulation must  
73 range from 0 to 10 mm and 10 to 20 degrees in the oblique plane, respectively.

74

75 *Exclusion criteria*

76

- 77 • Polytrauma (Injury Severity Score  $\geq$  16)
- 78 • A concomitant fracture in the same limb
- 79 • Pathologic/open fracture
- 80 • Neuromuscular/metabolic bone diseases
- 81 • Concomitant neurologic/vascular lesions
- 82 • Longitudinal limb deficiency
- 83 • Previous infection/fracture in the fractured radius

84

85 *Randomization*

86

87 Randomization will be performed centrally by the Instituto Roosevelt Medical Research  
88 Department. Therefore, allocation will be concealed to the orthopedic surgeons. The Big Stick  
89 Design (BSD) with a maximum tolerated imbalance of 2 will be the methodology for  
90 randomization. The BSD has a very low probability of correctly guessing the allocation of the  
91 next child compared to other designs[11]. The R and RStudio statistical software, specifically the  
92 randomizeR package version 4.1, will be used[12].

93

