#### 121 *Power analysis and sample calculation*

122

123 In a personal communication, [name] provided PROMIS range scores (36 to 39), variability  
124 (SD=10) and the minimally clinical important difference (MCID; 3 to 5) in children who have  
125 sustained an upper extremity fracture[14]. Therefore, assuming a non-inferiority threshold of 5,  
126 the trial requires a sample of 126 children (63 per group) to demonstrate no meaningful  
127 difference in the primary outcome (one-tailed  $\alpha=0.05$ ,  $\beta=0.2$ ). The sample will be inflated to  
128 152 (20%) due to the anticipation of loss to follow-up.

129

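### Does a maximum tolerated imbalance of 2 make the allocation sequence too predictable for a one-centre, open-label trial?

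*Combined protocol and SAP*

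**What the plan says.** The subsection Randomization says that the institution's research department randomizes centrally, and it draws the consequence for concealment: "Department. Therefore, allocation will be concealed to the orthopedic surgeons". It sets the method and the limit ("Design (BSD) with a maximum tolerated imbalance of 2 will be the methodology for" the sequence) and supports the design with one argument: "The BSD has a very low probability of correctly guessing the allocation of the" "next child compared to other designs[11". It gives no guess rate, names no strata and does not say why the limit is 2.

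Other sections supply the setting. Study design and procedures describes "a single institution that focuses on providing treatment for children with orthopedic" and neuromuscular conditions, where "afterwards, the principal researcher will invite children and parents to enter into the trial upon" confirmation of the entry criteria. Inclusion criteria asks that shortening and angulation "range from 0 to 10 mm and 10 to 20 degrees in the oblique plane, respectively". Interventions sets a 1:1 ratio and reserves general anesthesia for the control arm. Power analysis and sample calculation raises the sample to "152 (20%) due to the anticipation of loss to follow-up". Data management limits registry access to the principal researcher and the study conductor. Schedule dates the start of recruitment to June 2021, at about ten children a month. Discussion states that patients, parents and staff know the treatment, while the analysis of results is blinded.

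**The concern.** Under the Big Stick Design each child is allocated by a fair coin until the arms differ by the limit; the next child must then go to the smaller arm. A small limit makes such forced steps frequent. Central randomization hides the list, but it cannot hide a forced step from someone who knows the limit and has counted the earlier allocations. Here the limit is printed in the protocol, there is one site, treatment is visible, and the principal researcher both enrols children and has registry access.

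If the next arm could be foreseen when a family is invited, children might be steered into or away from the trial. A blinded analysis could not undo that selection, and the primary outcome is reported by an unblinded parent or child. Because low guessability is the only argument given for the design, a limit that produces many forced steps seems to defeat its purpose. Loosening it costs almost no power, so a limit of 4 or 5 looks like an easy gain.

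**Working it through.** **Inputs.** Limit 2 (Randomization); 1:1 ratio (Interventions); 152 children, margin 5, SD 10 (Power analysis and sample calculation); start in June 2021 at ten a month (Schedule). The plan's total reproduces as 126 × 1.20 = 151.2, rounded up to 152. The plan gives no figure for forced steps or guess rate.

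**Forced steps at limit 2.** Before every odd-numbered allocation the imbalance is 0 or ±2. From 0, two fair steps end at ±2 with probability 1/2. From ±2, one forced step and one fair step also end at ±2 with probability 1/2. So each odd-numbered allocation from the third to the 151st is forced with probability 1/2. There are (151 − 3)/2 + 1 = 75 of them, and 75 × 0.5 = 37.5, which is 24.7% of 152.

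**Guess rate.** Someone who always guesses the smaller arm is right on every forced step and on half of the rest, so the rate is 0.5 + 0.5 × forced share. The same exact chain for other limits, applied from the first child, gives:

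| Limit | Expected forced steps | Share | Correct guesses |
|---|---|---|---|
| 2 | 37.5 | 24.7% | 62.3% |
| 3 | 24.9 | 16.4% | 58.2% |
| 4 | 18.25 | 12.0% | 56.0% |
| 5 | 14.4 | 9.5% | 54.7% |

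**Against permuted blocks.** Over the six sequences of a block of 4, which has the same maximum imbalance of 2, 8 of 24 allocations are determined (33.3%) and 17 of 24 guesses are right (70.8%). Listing all sequences for blocks of 6 and 8 gives 82/120 = 68.3% and 373/560 = 66.6% right. Blocks of 8 have a smaller determined share (20.0%) than limit 2, but they allow an imbalance of 4 and are still guessed more often.

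**What a change could still achieve.** Recruitment is open, so the rows for limits 4 and 5 above cannot be attained for the whole trial. Keeping limit 2 for the first m children and carrying the imbalance over gives, for the whole trial:

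| Change after | Forced, limit 4 / 5 | Correct guesses, limit 4 / 5 |
|---|---|---|
| 38 | 22.75 / 19.8 | 57.5% / 56.5% |
| 76 | 27.5 / 25.5 | 59.0% / 58.4% |
| 114 | 32.25 / 31.2 | 60.6% / 60.3% |

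For example, at 76 with limit 4: 18.5 + 9.0 = 27.5; 27.5/152 = 18.1%; 0.5 + 0.5 × 0.181 = 59.0%. Forced steps still to come are cut by at least 51% (limit 4) or 62% (limit 5) at every change point examined. That proportion says little about benefit: with 12 children left, limit 4 lowers the expected count only from 3.0 to 1.0.

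**What the tight limit buys.** In simulated lists with entry order scaled 0 to 1, the SD of the arm difference in mean entry order is about 0.010 at limit 2, 0.018 at limit 4 and 0.022 at limit 5. The same figures are the SD of bias from a linear drift, as a fraction of the total drift. A limit of 2 roughly halves that exposure. Tight balance adds almost no power: 63 versus 63 analysed gives 0.8741 and 61 versus 65 gives 0.8738 at one-tailed 0.05 (0.7952 and 0.7948 at one-sided 0.025).

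**Size of any bias.** The documents give no basis for a figure. Assume for illustration that steering shifts a child's expected score by 0.5 to 2 points and that every forced slot is exploited in both directions. The ceiling is 2 × shift × forced share: at limit 2, 2 × 0.5 × 0.247 = 0.25 up to 2 × 2 × 0.247 = 0.99 point. After a change to limit 4 at 76 it is 0.18 to 0.72. The gain is 0.07 to 0.26 point against a margin of 5, and half that if half the slots are exploited.

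**Time left.** 152 / 10 is about 15 months, so from June 2021 the plan's own pace ends recruitment around September 2022. Current enrolment is not given.

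**The case for a change.** The strongest case for changing the limit is that the ingredients of selection bias are all present. There is one centre, one unstratified list, a published limit, visible treatment, and a principal researcher who enrols and can open the registry. The outcome is self- or proxy-reported without blinding, so concealment before allocation is one of the few protections left. The protocol neither justifies 2 nor quantifies predictability, and a wider limit costs at most 0.04 percentage point of power. At the design stage a statistician could well have preferred 3 or 4.

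That much stands as a preference, but it does not make the choice of 2 wrong. The route to harm is not documented: nothing says that anyone who enrols keeps a tally, or that allocations are visible in the registry when the next family is invited. Invitation follows confirmation of criteria set largely in years, fracture class, millimetres and degrees, which leaves less room for steering. A wider limit is also only a partial remedy, because guessing the smaller arm needs no knowledge of the limit. And power is not the whole price: a change means altering the algorithm of a running trial, a possible amendment before two ethics committees, two randomization regimes to report, and weaker protection against drift.

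**Conclusion.** The concern does not hold. Limit 2 does imply 37.5 expected forced allocations among 152, but that is a property of a legitimate choice between balance and predictability. The protocol's claim is comparative, and it is borne out against permuted blocks of 4, 6 and 8 (62.3% correct guesses against 70.8%, 68.3% and 66.6%). The gain still available from a wider limit is modest: 3.3 or 3.9 percentage points in guess rate if made at child 76 (62.3% to 59.0% or 58.4%), about 2 if made at child 114 (to 60.6% or 60.3%), and none once recruitment has closed. Statisticians could reasonably differ on whether that justifies a mid-trial change, so the plan need not be altered.

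These figures assume a single unstratified list, all 152 children randomized, and a guesser who knows every earlier allocation. The documents do not establish the last of these. The conclusion would need another look if there were evidence that the person inviting families tracked the allocations.

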#### 94 *Interventions*

95

96 Patients will be allocated in a 1:1 ratio to either the experimental or control group. In the  
97 former, fractures will be immobilized without reduction. In the latter, fractures will be reduced  
98 and immobilized. Provided instability, K-wires will be used. Instability is considered when, after  
99 reduction, alignment is lost: a new displacement or angulation larger than 50% and 10 degrees,  
100 respectively. General anesthesia will be mandatory exclusively for the control group. Discharge  
101 within two hours is the standard practice for both procedures. Plain radiographs will be  
102 obtained immediately after the intervention, at two weeks, three-, and nine-months during  
103 follow-up. Casts and K-wires will be removed at 6 weeks.

104

#### 105 *Endpoints and follow up*

106

107 Children will be evaluated at about two and six weeks, three, six, and nine months after  
108 randomization. The primary endpoint is the upper extremity function assessed with the

109 PROMIS Pediatric Physical Function v2.0 at six months. Parents will serve as proxies of children  
110 <8 years with the proper format of the scale. From 8 years of age onwards, children will  
111 personally answer the questionnaire.

112  
113 The secondary outcomes are the ROM, ulnar variance, and fracture alignment in the sagittal  
114 and coronal planes. Plain radiographs of the wrist at two weeks, three and nine months and a  
115 standard goniometer will be used. Additionally, general anesthesia-related adverse effects,  
116 pressure ulcers according to the National Pressure Ulcer Advisory Panel, the number of days of  
117 required oral analgesics and Dahl classification of pin tract infections will also be registered[13].  
118 Further treatments such as radius osteotomy due to deformity, pseudoarthrosis cure, and  
119 remanipulation will also be recorded. Figure 1 depicts the flow of the study.

120

#### 121 *Power analysis and sample calculation*

122

123 In a personal communication, [name] provided PROMIS range scores (36 to 39), variability  
124 (SD=10) and the minimally clinical important difference (MCID; 3 to 5) in children who have  
125 sustained an upper extremity fracture[14]. Therefore, assuming a non-inferiority threshold of 5,  
126 the trial requires a sample of 126 children (63 per group) to demonstrate no meaningful  
127 difference in the primary outcome (one-tailed  $\alpha=0.05$ ,  $\beta=0.2$ ). The sample will be inflated to  
128 152 (20%) due to the anticipation of loss to follow-up.

129

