#### 130 *Data management*

131

132 Participant's information will be recorded in the REDCap software. Registries will be password-  
133 protected with access granted just to the principal researcher and the study conductor. Data  
134 will be kept at the Instituto Roosevelt Medical Research Department. After completing the  
135 study, data will be preserved for two years, then all non-anonymized documents will be  
136 discarded.

137

138 *Statistical analysis*

139

140 Customary descriptive statistics will be used whether the variables are continuous or  
141 categorical. The intention-to-treat principle will be followed in this trial. Authors of the scale in  
142 the Northwestern University will standardize PROMIS scores once data gathering is completed,  
143 afterwards, the primary outcome will be evaluated with a t-test. The non-inferiority threshold  
144 will be compared to the lower bound of the 95% confidence interval of the mean difference.  
145 Secondary outcomes measured with continuous variables (i.e., ROM, ulnar variance, fracture  
146 alignment and number of days with oral analgesia) will be compared with the t-test or Mann-  
147 Whitney's U conforming to the distribution of the variables. Categorical outcomes will be  
148 compared with the Fisher's exact test (i.e., anesthesia-related adverse effects, pressure ulcers,  
149 pin tract infections, radius osteotomies, pseudoarthrosis, and remanipulations). Early  
150 termination of the trial is unlikely; therefore, interim analyses are not considered: given the  
151 proposed design, neither superiority nor futility of the experimental treatment is expected.

152

153 *Schedule*

154

155 Recruitment commenced in June 2021. The principal researcher personally interviews parents  
156 and children and the trial's general characteristics are completely explained. Benefits, such as a  
157 close follow-up (e.g., radiographs, pain, functionality) are also explained. Authors expect an  
158 average of ten patients monthly, therefore, recruitment and analysis should be complete by  
159 June 2023.

160 O?

161 *Declarations*

162

163 Both, Instituto Roosevelt and Pontificia Universidad Javeriana Ethics Committees, evaluated  
164 and accepted trial's protocol, research manual, consent and assent forms, and information  
165 brochures (approval No. 2021012101-002 and FM-CIE-0416-21, respectively). The datasets used  

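### Does setting the margin at 5, the top of the stated MCID range of 3 to 5, undermine the non-inferiority claim?

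*Combined protocol and SAP*

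**What the plan says.** Under Power analysis and sample calculation, the protocol takes three inputs from a personal communication about children with upper extremity fractures: the range of PROMIS scores, an SD of 10, and "the minimally clinical important difference (MCID; 3 to 5" points. The margin follows directly: "Therefore, assuming a non-inferiority threshold of 5". The same sentence says that "the trial requires a sample of 126 children (63 per group) to demonstrate no meaningful" difference in the primary outcome, at one-tailed alpha 0.05 and beta 0.2.

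Under Statistical analysis, the threshold "will be compared to the lower bound of the 95% confidence interval of the mean difference". This is the only success rule. The goal, at the end of Functional evaluation, is to establish that function after casting in situ "is not worse than the functionality of children treated with closed reduction".

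The documents do not say why 5 was preferred to 3 or 4, how the range 3 to 5 should be read, or whether any second margin will be considered.

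**The concern.** If the smallest difference that matters could be as low as 3 points, ruling out 5 does not rule out a difference that matters. A trial could meet its criterion while its interval still contained deficits of 3 or 4 points, yet be described in the terms of the sample-size sentence as having shown no meaningful difference. The quoted 80% power would then belong only to the lenient end of the range.

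The protocol calls this the first randomized trial to compare functional outcomes of non-reduced and reduced distal radius fractures in children, and it hopes to inform treatment boundaries. An overstated headline could therefore carry weight in practice.

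**Working it through.** **Inputs.** From the protocol: margin 5, MCID 3 to 5, SD 10, 63 per group (126 in total), 152 after inflation, power 80%, 1:1 allocation, and the lower bound of a 95% confidence interval as the decision quantity. Assumed here: a true difference of 0 for power, and a higher score meaning better function. Results are given at one-sided 0.025 (the lower bound of a two-sided 95% interval), with one-sided 0.05 in brackets.

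**The protocol's own figure.** n per group = 2 × SD² × (z for alpha + z for power)² / margin².

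- One-sided 0.025: 2 × 100 × (1.960 + 0.842)² / 25 = 62.8, so 63 per group and 126 in total. This matches.
- One-sided 0.05: 2 × 100 × (1.645 + 0.842)² / 25 = 49.5, so 50 per group and 100 in total. This does not match.

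The gap between the stated alpha and the one that reproduces 126 is a separate point. Both levels are carried below because the conclusion is the same under each. The inflated figure is 126 × 1.2 = 151.2, rounded up to 152.

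**Precision.** Standard error = 10 × √(2/63) = 1.782, with 124 degrees of freedom. The interval half-width is 3.53 (2.95). The largest observed deficit that still passes is 5 − 3.53 = 1.47 points (5 − 2.95 = 2.05).

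**Probabilities, from the noncentral t distribution with 63 per group:**

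| Quantity | One-sided 0.025 | One-sided 0.05 |
|---|---|---|
| Power to exclude a 5-point deficit, true difference 0 | 79.5% | 87.4% |
| Power to exclude a 3-point deficit, true difference 0 | 38.6% | 51.2% |
| Declared non-inferior when the true deficit is 3 | 19.9% | 29.9% |
| Declared non-inferior when the true deficit is 4 | 8.0% | 13.9% |

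If all 152 children are analysed (76 per group), power to exclude 3 points is 45.1% (57.8%).

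**Passing trials whose interval still contains a 3-point deficit, true difference 0.** (79.5 − 38.6) / 79.5 = 51% at 0.025, and (87.4 − 51.2) / 87.4 = 41% at 0.05. Letting the SD run from 8 to 12 (an assumed range) and the group size from 63 to 76 widens this to about 25% to 56%.

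**What a stricter margin would cost.** With margin 3, 2 × 100 × (1.960 + 0.842)² / 9 = 174.4, so 175 per group and 350 in total (276 in total at one-sided 0.05), before any allowance for loss to follow-up.

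**The case for a change.** The best case for a change is that the protocol claims more than its rule delivers. It lists 3 as a possible MCID, sizes the trial for 5, gives no reason for taking the upper end, and states the purpose as though the whole range were covered. Under an interval read as two-sided, even an observed difference of exactly zero gives a lower bound of −3.53, so excluding 3 points would require casting to look about half a point better. Correcting this would take a few words and no extra patients.

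Part of this stands. The upper end of the range is not justified, and the purpose statement is broader than the rule if the MCID is below 5. The 20% to 30% chance of passing with a true 3-point deficit is the most serious figure.

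The rest is weaker:

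- The margin is not unanchored: the word opening "Therefore, assuming a non-inferiority threshold of 5" ties it to the MCID just reported, and 5 is defensible if that is the MCID. The documents do not say whether 3 to 5 expresses uncertainty about one threshold, variation between methods, or a band in which every value matters.
- The broad phrase is not a rule for conclusions. The rule is in Statistical analysis, and the stated goal uses ordinary non-inferiority language. Nothing in the documents plans a report that omits the margin.
- The 41% to 51% figure concerns trials in which the treatments are truly equal, so the verdict of non-inferiority is correct. An interval reaching −3 there shows limited precision, as it would in any trial sized for a larger margin.
- Making an unqualified conclusion depend on excluding 3 points would act as a second hurdle with 39% to 51% power. Statisticians can reasonably disagree about that.

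**Conclusion.** The observation is accurate: success excludes a true deficit of 5 points or more and leaves deficits of 3 to 5 open, with power of only 39% to 51% against 3 points if the treatments are equal. It does not lead to a change in the plan. A margin inside the stated MCID range, in a trial of 126 evaluable children rather than 350 (or 276), is a fair trade-off. It also has a built-in safeguard: no trial passes with an observed deficit above about 1.5 to 2.0 points, which is below the bottom of the MCID range.

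What is missing is one sentence of rationale and a more exact description of what the sample can show. Supplying either would alter no margin, sample size, test or decision. The interval is already planned, so anyone who regards 3 points as important can read it against 3.

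The figures assume an SD of 10, 63 evaluable children per group and higher scores meaning better function. The conclusion holds at either alpha. It would need revisiting if the final report claimed no meaningful difference without stating the margin, but nothing in the documents commits the authors to that.

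### 63 children per group follows from a one-tailed alpha of 0.025, not the stated 0.05, so the error rate of the primary non-inferiority test is given two ways

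*Combined protocol and SAP*

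**What the plan says.** The section on power analysis and sample calculation gives an "assuming a non-inferiority threshold of 5" points and a PROMIS SD of 10. It then says that "the trial requires a sample of 126 children (63 per group) to demonstrate no meaningful" "difference in the primary outcome (one-tailed" alpha 0.05, beta 0.2). The total of 126 is afterwards raised to "152 (20%) due to the anticipation of loss to follow-up". No expected true difference between the arms is given there.

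The Statistical analysis section has the primary outcome evaluated by t-test and gives the only decision rule: the non-inferiority threshold "will be compared to the lower bound of the 95% confidence interval of the mean difference". It does not say whether that interval is one-sided or two-sided, which arm is subtracted from which, or what sign the threshold carries.

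**The concern.** Alpha, sample size and decision rule should be three expressions of one test. Here the sample size does not follow from the alpha printed beside it, and the decision rule agrees with one or the other depending on how the interval is read.

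This is the primary confirmatory comparison. If it is unclear whether the one-sided error rate is 5% or 2.5%, the same data could be reported as showing non-inferiority under one reading and as not showing it under the other. That choice has to be settled before results are known, and nothing else in the protocol settles it.

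**Working it through.** **Inputs.** Margin 5, SD 10, one-tailed alpha 0.05, beta 0.2 and 63 per group all come from the power section. Equal allocation comes from Interventions ("Patients will be allocated in a 1:1 ratio to either the experimental or control group"). The true difference is not stated, so I take it as zero. That is the usual planning assumption for non-inferiority and fits the remark in Statistical analysis that "proposed design, neither superiority nor futility of the experimental treatment is expected".

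**Formula.** n per group = 2 × (z_alpha + z_beta)² × SD² / margin², so SD²/margin² = 100/25 = 4.

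**Reproducing the plan's figure.**
- One-tailed 0.025: 2 × (1.960 + 0.842)² × 4 = 62.79 with unrounded quantiles, so **63 per group, 126 in total**. This matches the plan exactly.
- One-tailed 0.05, as stated: 2 × (1.645 + 0.842)² × 4 = 49.46 with unrounded quantiles, so **50 per group, 100 in total**.
- Exact noncentral-t versions: 64 per group at 0.025 and 51 at 0.05.

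**Other routes to 63 at one-tailed 0.05.** Holding the remaining inputs fixed, one of these would be needed:
- a true deficit of about 0.57 points in the cast-only arm;
- an SD of about 11.29;
- a margin of about 4.43.

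None of these is in the protocol. Other variants at one-tailed 0.05 also miss:

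| Variant | n per group |
|---|---|
| Power 85% / 90% | 58 / 69 |
| Margin 4 / 3 | 78 / 138 |
| Mann-Whitney efficiency 0.955 / 0.864 | 52 / 58 |
| Equivalence test (TOST) | 69 |

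Finally, 50/0.8 = 62.5 rounds up to 63, but the plan inflates 126 for loss to follow-up in the next sentence, so this would count dropout twice.

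**Power with 63 per group.**

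| One-tailed alpha | Normal approximation | Exact t |
|---|---|---|
| 0.05 | 87.7% | 87.4% |
| 0.025 | 80.1% | 79.5% |

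**Effect on the verdict.** The standard error is 10 × √(2/63) = 1.78. The largest observed deficit that still passes is 5 minus the critical value times 1.78:

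| Rule | Normal critical value | t critical value (124 df) |
|---|---|---|
| Two-sided 95% interval (0.025) | 1.51 | 1.47 |
| One-tailed 0.05 | 2.07 | 2.05 |

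So, by t-test, observed deficits between 1.47 and 2.05 points change verdict with the reading. If the arms are truly equal, the chance of landing in that band is the difference between the two powers: 87.4% − 79.5% = 7.9%.

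**The case against.** The strongest reply is that the plan has only one decision rule, the one in Statistical analysis, and that the alpha in the power section is merely a planning input. On the ordinary two-sided reading of a 95% interval, every result has a defined verdict at one-sided 0.025. On that view the defect is a misprinted planning figure that harms nobody, since power before dropout is about 80% or more at either level.

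Part of this stands. The trial is not materially underpowered by the mismatch, and the rule is better called ambiguous than undefined. But the sidedness of the interval is nowhere stated, and the only explicit statement about tails in the protocol is one-tailed 0.05. A reader who applies that to the 95% limit gets a one-sided bound and a different test.

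It can also be said that 63 is reconcilable with 0.05 if a small true deficit or a larger SD was assumed. That is arithmetically correct, but neither assumption is documented, whereas 0.025 reproduces 63 with every stated input unchanged. That 0.025 was intended remains an inference, though a well-supported one.

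**Conclusion.** The concern holds. With the stated margin, SD and beta, and a true difference of zero, one-tailed alpha 0.05 requires 50 per group (51 by t-test), 13 fewer than the 63 given. The 63 belongs to one-tailed 0.025. Using only the stated inputs and a zero difference, no reading makes alpha, sample size and decision rule agree: a two-sided 95% interval fits 63 but not the stated alpha, and a one-sided 95% bound fits the alpha but not 63.

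The consequence is a twofold uncertainty in the permitted false-positive rate and a band about 0.6 points wide, on a 5-point margin, in which the conclusion depends on the reading. The band limits assume SD 10 and 63 analysed per group; they will shift with the observed SD and the numbers analysed. Because this concerns the primary success criterion, it must be corrected even though the sample size itself can stand.

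**What to change.** Two sentences change:

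- **Power analysis and sample calculation:** replace the one-tailed alpha of 0.05 with one-tailed 0.025, and state that the true difference is assumed to be zero.
- **Statistical analysis:** state that non-inferiority is concluded if the lower limit of the two-sided 95% confidence interval for the mean difference (cast only minus reduction) lies above -5, and that higher PROMIS scores mean better function. The plan's use of the lower limit implies that scoring direction, but it is not stated.

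Keep 63 per group. It is worth noting that 63 is the normal-approximation figure and that the exact t calculation gives 64.

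If one-tailed 0.05 was truly intended, the consistent alternative is to name a one-sided 95% bound (equivalently, a two-sided 90% interval), correct the requirement to 50 per group (51 by t-test), and describe 63 as a deliberate excess. The first route is simpler and fits the figures already in the plan.

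Either way the cost is wording only, with no change to the number of children. The choice should be recorded and dated before any comparison of the arms is seen.
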